4.3.2. Individual Stopping Rules

This is a single dose trial, therefore, there are no individual stopping rules.

4.4. Subject Withdrawal

4.4.1. Subject Withdrawal from Trial

If a subject is withdrawn from the trial, the Sponsor will be informed immediately, and the subject will be considered an early-termination subject.

If there is a medical reason for withdrawal, the subject will remain under the supervision of the Investigator until the medical situation has resolved.

Regardless of the reason for withdrawal, the Investigator will make every effort to ensure that early-termination subjects who have received any IMP complete the necessary safety follow-up assessments at an EOT visit.

Reason for withdrawal and the date of discontinuation from the trial will be documented under the following categories:

- It is the wish of the subject to withdraw, for whatever reason
- The Investigator judges it necessary due to non-compliance with trial procedures or administrative reasons (including if the subject loses the ability to give consent)
- The Investigator judges it necessary to protect the subject's best interest (including safety concerns related to AEs)
- Medical considerations have emerged including difficulties with obtaining or completing required protocol assessments that, in the opinion of the Investigator, potentially affect the safety of the subject. For example, this may include inability to obtain blood samples for safety assessments
- The subject is pregnant
- The clinical trial is terminated by the Sponsor

4.4.2. Subject Withdrawal from Investigational Medicinal Product

If a subject is withdrawn from the trial, all attempts will be made to ensure a final safety visit (EOT) will be conducted as per the Schedule of Events ([Table 1](#)).

For all withdrawn subjects who have been dosed with the IMP, EOT assessments will be performed at an early termination visit performed as soon as possible after the dose. The Investigator will document the date of discontinuation of trial treatment and, if possible, the main reason for the subject's withdrawal or discontinuation in the subject's medical record.

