4. TRIAL DESIGN

4.1. Summary of Trial Design

4.1.1. Trial Design

This is a Phase 1, non-randomized, open-label, single-dose trial to evaluate the effect of impaired hepatic function on the PK, safety, and tolerability of apaglutide administered to trial subjects by SC injection.

Subjects with mild hepatic impairment (Child-Pugh A) and moderate hepatic impairment (Child-Pugh B) will be enrolled. Patients with decompensation, late-stage cirrhosis, and cirrhosis-related complications (Child-Pugh C) will not be included in this trial, as such patients are not envisioned to be treated chronically with apaglutide. A staged approach will be followed in the trial. Part 2 of the trial will be conducted after evaluation of Part 1 if the geometric mean ratio (GMR) point estimate of apaglutide AUC_{inf} or AUC_{last} for the moderate hepatic impairment group compared to the control group is ≥ 2 . If this criterion is not met, the trial will stop after Part 1. Subjects will be selected and categorized into normal hepatic function, or hepatic impairment groups based on their Child-Pugh score ([Table 2](#)).

Subjects withdrawn or discontinued from treatment in the normal, mild, or moderate hepatic impairment groups and are considered to be non-evaluable, with respect to the primary PK objective, can be replaced at the discretion of the Sponsor.

Following consent, subjects will undergo a Screening procedure to determine their suitability for trial enrollment. Screening will occur within a 28-day window prior to dosing. Subjects will be admitted on Day -1. On Day 1 a single SC injection of 5 mg apaglutide will be administered. The subjects will remain at the Clinical Research Unit (CRU) post-dose and either will be discharged on Day 11 or will be allowed to leave the center on Day 8 and will be asked to come back on Day 11 for an outpatient visit. Pharmacokinetics will be assessed on Days 1 to 8, Day 11 and Day 14. The EOT visit will take place on 14 ± 2 days. Pharmacokinetics of blood samples will be assessed for 312 hours (until Day 14 inclusive). Subjects who received apaglutide (except subjects who exit from the trial early) will return to the CRU approximately 14 ± 2 days after dosing for the EOT visit where follow-up assessments will be performed according to the Schedule of Assessments ([Table 1](#)) and to determine if any AEs have occurred since the last trial visit.

[figure not shown]
The trial schematic diagram is shown in [Figure 2](#).

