4.1.3. Duration of Subject Participation

The planned length of the trial is up to 42 ± 2 days (from Screening through trial completion) for each enrolled subject.

Screening period: Lasts a maximum of 28 days; starts with the full signature (subject and Investigator/delegate) of the ICF and ends with the subject's enrollment or screening failure.

Treatment period: Starts and ends with the administration of a single apaglutide dose.

Post-treatment observation period: Starts on Day 1, the day of dosing of apaglutide, and ends 14 ± 2 days after the dose of apaglutide. For the first 8 days, the subjects will remain at the CRU.

Safety follow-up period: Starts the day after the dose of apaglutide and ends 14 ± 2 days later with the EOT visit. Subjects with AEs related to the investigational medicinal product (IMP) will be followed up until resolution or until deemed unresolvable.

The subject is expected to participate in the trial for a duration of up to 14 ± 2 days.

The visit schedule and protocol-mandated procedures are performed according to the Schedule of Events ([Table 1](#)).

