11. ADVERSE EVENTS AND SERIOUS ADVERSE EVENTS

11.1. Adverse Events

An AE is any untoward medical occurrence in a patient or clinical investigation subject administered a pharmaceutical product that does not necessarily have a causal relationship with this treatment. An AE can therefore be any unfavorable and unintended sign (including an abnormal laboratory finding), symptom, or disease temporally associated with the use of a medicinal (investigational) product, whether or not related to the medicinal (investigational) product.

Adverse events will be collected for all subjects from when the ICF is signed until the EOT visit.

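### The protocol contradicts itself on when safety follow-up ends for dosed subjects who leave early, so new adverse events could go uncollected before the 14±2-day window

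*Protocol*

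**What the plan says.** Five statements in the protocol bear on a dosed subject who leaves early.

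- Section 4.1.3, on the safety follow-up period: "Starts the day after the dose of apaglutide and ends 14 ± 2 days later with the EOT visit".
- Section 4.4.2, first sentence, for a withdrawn subject: "all attempts will be made to ensure a final safety visit (EOT) will be conducted as per the Schedule of Events".
- Section 4.4.2, second sentence, for withdrawn subjects who have been dosed: "EOT assessments will be performed at an early termination visit performed as soon as possible after the dose".
- Section 4.1.1: "Subjects who received apaglutide (except subjects who exit from the trial early) will return to the CRU" about 14±2 days after dosing for the EOT visit.
- Section 11.1: "Adverse events will be collected for all subjects from when the ICF is signed until the EOT visit".

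Two provisions extend follow-up for particular problems. Section 4.4.1 states: "If there is a medical reason for withdrawal, the subject will remain under the supervision of the Investigator until the medical situation has resolved". Section 4.1.3 states that subjects with AEs related to the investigational product "will be followed up until resolution or until deemed unresolvable". Section 4.4.1 also asks for every effort to complete the safety assessments at an EOT visit whatever the reason for withdrawal, but does not say when that visit falls.

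**The concern.** In a single-dose trial, leaving early does not shorten exposure. The subject has already had the whole dose of a peptide designed for a longer half-life (Protocol 1.1.1) and sampled for PK to 312 hours. If the EOT assessments are done soon after dosing, the later return is waived and AE collection closes at EOT, a site could reasonably close the subject at the early visit. A new event in the following days would then have no stated route into the database.

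Safety and tolerability is the secondary objective. The Safety Set keeps every dosed subject, and SAP 9.1.3 bases percentages on subjects exposed. An early leaver therefore counts fully in the denominator with only part of the planned observation. In a cohort of eight, one subject is 1/8 = 12.5%.

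Sponsor termination needs particular attention. It is a withdrawal category in 4.4.1, and 4.1.5 and 4.3.1 name early evidence of harm and unacceptable risk among the grounds for stopping. On that route, the second sentence of 4.4.2 could shorten follow-up for every dosed subject still inside the window, at a time when there is a safety question.

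**Working it through.** **The plan's own figure.** Section 4.1.3 gives a screening period of at most 28 days and follow-up to 14±2 days after the dose. 28 + 14 = 42, range 28 + 12 = 40 to 28 + 16 = 44. This reproduces the stated 42±2 days, so the planned duration assumes that follow-up runs to the full window.

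**The statements side by side.** Section 4.1.3 and the first sentence of 4.4.2 point to the full window. The second sentence of 4.4.2, the exemption in 4.1.1 and the closing point in 11.1 together point to an earlier close. Table 1 does not settle the matter, because its last column is headed both 14±2 days and End of Trial/Early Termination. No section gives a minimum interval between dose and early visit, or a separate end date for recording new AEs in early leavers.

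**Size of the possible gap.** Day 1 is the dosing day, so a visit on study Day d falls d − 1 days after the dose. If recording of new AEs ends at that visit, the shortfall is W − (d − 1), with W = 12, 14 or 16 days after the dose. The visit days below are assumptions, since the documents give no withdrawal times.

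| Early visit | Days after dose | Short of opening (12) | Short of nominal (14) | Short of close (16) |
|---|---|---|---|---|
| Day 2 | 1 | 11 | 13 | 15 |
| Day 3 | 2 | 10 | 12 | 14 |
| Day 5 | 4 | 8 | 10 | 12 |
| Day 8 | 7 | 5 | 7 | 9 |
| Day 11 | 10 | 2 | 4 | 6 |

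Reading the window as study Days 12 to 16 lowers every shortfall by one day. If recording ran to the window for every dosed subject, the shortfall would be zero.

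**Scheduled assessments.** By the footnotes to Table 1, laboratory tests and ECGs fall on Days 2, 8, 11 and EOT. A subject closed out on Day 3 would miss the Day 8 and Day 11 sets, and the EOT set would be taken on Day 3.

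**What the extended follow-up covers.** The provision in 4.4.1 runs until the medical situation behind the withdrawal has resolved. The one in 4.1.3 covers AEs related to the product. Both attach to an identified problem, and neither says that new, different events continue to be recorded. Exits at the subject's wish, for non-compliance or for administrative reasons have no stated follow-up after the early visit unless there is a related AE.

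**The case against.** A reader might infer that safety follow-up is abandoned in the very subjects who leave because of an AE. The documents do not support that. Section 4.4.1 gives medical withdrawals open-ended supervision, 4.1.3 follows related AEs without a day limit, and 11.3 requires proactive follow-up information on SAEs. This part of the objection stands in full.

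It can also be said that no section states that AE collection closes at the early visit. Section 11.1 refers to the EOT visit, 4.1.3 places that visit at 14±2 days, and 4.4.2 uses a separate term for the early visit. That is right: the early close is an inference. It is nevertheless a reasonable one, because the early visit carries the EOT assessments and the later return is waived.

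The practical effect may be small. Subjects stay in the unit for the first 8 days, so an earlier exit means leaving a residential stay. Section 1.3.1 considers most class effects unlikely after a single dose, and the safety analysis is descriptive. SAP Appendix 3 already plans listings of subject disposition, study dates and AEs leading to withdrawal, which should largely show any shortened observation. These points limit the consequences and make a further SAP listing unnecessary. They do not remove the contradiction.

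**Conclusion.** The contradiction is real and worth correcting, but narrow. Followed literally, one set of statements could end the recording of new AEs, and the scheduled safety assessments, before the window that 4.1.3 sets. The gap is 2 to 11 days short of window opening for assumed early visits between Day 11 and Day 2. It concerns new events in any dosed early leaver, and exits for non-medical reasons or by sponsor termination. It does not concern the event behind a medical withdrawal or AEs related to the product.

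The number of subjects affected cannot be computed and may be zero. A reader might infer 0 to 2 per cohort from enrolling eight to secure six evaluable, but that allowance concerns PK evaluability; a subject can be non-evaluable for PK and still complete safety follow-up. A reader might also infer that AE rates are biased between hepatic function groups. That would require unequal early withdrawal and new events falling in the unobserved days, and the documents give no information on either.

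**What to change.** Reconcile the two sentences of 4.4.2 with each other and with 4.1.1, 4.1.3, 4.4.1 and 11.1, and replace the wording that ties the early visit to the earliest moment after dosing. State one end point for collecting new AEs in dosed subjects who leave early, consistent with the follow-up window the protocol already sets and subject to the subject's consent. The text should make clear that it also covers exits for non-medical reasons and by sponsor termination. This review proposes no particular visit, laboratory or ECG schedule; those are for the sponsor to settle.

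The cost is a change of protocol wording and possibly one further contact for a few subjects, some of whom may decline. The analysis needs no change.

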5. TRIAL POPULATION

5.1. Subject Population Description

The subject population will include subjects with hepatic impairment and subjects with normal hepatic function.

5.2. Number of Subjects

A total of approximately 16 to 32 subjects will be enrolled. In Part 1, approximately 16 subjects will be enrolled; approximately eight subjects with moderate hepatic impairment (Child-Pugh B; Cohort 1) and approximately eight subjects with normal hepatic function (Cohort 2) to ensure at least six evaluable subjects in each group. Subjects with normal hepatic function will be matched 1:1 for age (± 10 years), BMI ($\pm 15\%$), and sex (1:1) to subjects with moderate hepatic impairment.

If the decision criterion to proceed to Part 2 is met, approximately eight subjects with mild hepatic impairment (Child-Pugh A; Cohort 3) will be enrolled to ensure at least six evaluable subjects in each group. The matching will be a group matching for age, BMI, and sex, with approximately 50% of the subjects with normal hepatic function (Cohort 2) on both sides of the median for age and BMI of all subjects with hepatic impairment (Cohorts 1 and 3), and with approximately the same sex distribution of the normal hepatic function subjects (Cohort 2) as compared with all subjects with hepatic impairment (Cohorts 1 and 3). As many as possible of the matching controls enrolled into Part 1 will serve as matching controls for Part 2. Additional subjects with normal hepatic function may be enrolled in order to meet the given matching criteria when the last PK sample of the last subject with hepatic impairment has been taken.

5.3. Eligibility Criteria

5.3.1. Inclusion Criteria

All Subjects

1. Signed and dated ICF prior to any trial-mandated procedure
2. Male or female subjects aged from 18 to 75 years at the time of signing the ICF
3. Body mass index range from 18 to 35 kg/m² and a body weight more than 50 kg
4. Women of childbearing potential must agree to practice effective contraception and to use a highly effective method of contraception (see [Section 7.1.1](#)) during the trial and for 4 weeks after the EOT visit
5. Postmenopausal women. Postmenopausal status is defined as no regular menstrual bleeding for at least 12 months prior to inclusion. Menopause will be confirmed by a serum estradiol concentration of <20 pg/mL and a serum follicle-stimulating hormone (FSH) level of >40 IU/L

6. Male subjects with a female partner of childbearing potential must commit to practice highly effective methods of contraception (e.g., condom, vasectomy) and abstain from sperm donation during the trial and for 2 weeks after the EOT visit. Their partners, if they are women of childbearing potential, must agree to practice effective contraception and to use a highly effective method of contraception during the trial and for 4 weeks after the EOT visit. See [Section 7.1.3](#)
7. Able to participate, willing to give written informed consent, and comply with the trial restrictions
8. Negative result of SARS-CoV-2 polymerase chain reaction testing in the morning prior to admission to the CRU (Day -1)

Additional Inclusion Criteria for Subjects with Normal Hepatic Function (Cohort 2)

9. No clinically relevant abnormalities identified by a detailed medical history, full physical examination, measurement of heart rate, 12-lead ECG, and clinical laboratory tests

Additional Inclusion Criteria for Subjects with Impaired Hepatic Function (Cohorts 1 and 3)

10. Diagnosis of cirrhosis (due to parenchymal liver disease), which is confirmed and documented by medical history and at least one of the following: physical examination, hepatic ultrasound, computed axial tomography scan, magnetic resonance imaging, and/or liver biopsy
11. Cohort 1: moderate liver disease (Child-Pugh B) which has been clinically stable (defined as no clinically significant change in disease status) for at least 1 month prior to screening at the discretion of the Investigator
12. Cohort 3: mild liver disease (Child-Pugh A) which has been clinically stable (defined as no clinically significant change in disease status) for at least 1 month prior to screening at the discretion of the Investigator

5.3.2. Exclusion Criteria

All Subjects

1. History of clinically significant GI, bronchopulmonary, neurological, cardiovascular, endocrine, or allergic disease
2. Known hypersensitivity to the IMP, any of their excipients or drugs of the same class
3. If capable of reproduction, unwilling to use an effective form of contraception
4. If female of child-bearing potential, a positive urine/blood pregnancy test
5. Breast-feeding women
6. Positive urine/blood test for alcohol and drugs of abuse at Screening and on Day - 1

7. Use of prohibited medications or herbal remedies as detailed in [Section 10.2](#)
8. Known presence or history of intestinal polyps
9. Known presence or history of any type of cancer
10. Pancreatic events such as acute pancreatitis, pancreatic duct stenosis, pancreas infection, and increased blood amylase and lipase ($>2.0\text{--}5.0 \times$ upper limit of normal range)
11. Participation in an investigational drug or device study within 30 days prior to Screening
12. Donation of blood over 500 mL within 2 months prior to Screening
13. Heavy use of tobacco products (i.e., smokes more than 10 cigarettes per day)
14. Concomitant disease or condition that could interfere with, or for which the treatment of might interfere with, the conduct of the study, or that would, in the opinion of the Investigator, pose an unacceptable risk to the subject in this trial
15. Any intercurrent clinically significant illness in the previous 28 days before Day 1 of this study as determined by Investigator
16. Positive results to human immunodeficiency virus (HIV) antigen/antibody combo, hepatitis A (HAV), hepatitis B surface antigen (HBsAgB), or hepatitis C virus (HCV) tests. Subjects recovered from hepatitis B or C can be enrolled, i.e., they have markers of the infection, but the viral load is undetectable. Subjects with evidence of an acute or chronically active hepatitis B or C infection will be excluded. A subject being anti-HBs positive, with an undetectable viral load and with history of vaccination against hepatitis B are eligible for enrolment
17. Unwillingness or inability to comply with the study protocol for any other reason

Additional Exclusion Criteria for Subjects with Normal Hepatic Function (Cohort 2)

18. Any clinically relevant abnormal laboratory test results that are not in line with subject with normal hepatic function status at the discretion of the Investigator
19. Supine pulse rate less than 40 beats per minute (bpm) or more than 100 bpm at Screening. Supine systolic blood pressure below 90 mmHg or higher 140 mmHg. Supine diastolic blood pressure below 45 mmHg or higher than 90 mmHg at Screening

Additional Exclusion Criteria for Subjects with Impaired Hepatic Function (Cohort 1 and 3)

20. Any clinically relevant abnormal laboratory test results that are not in line with subject with stable liver disease status at the discretion of the Investigator
21. Supine pulse rate less than 40 bpm or more than 100 bpm at Screening. Supine systolic blood pressure below 100 or higher than 170 mmHg at Screening. Supine diastolic blood pressure below 60 mmHg or higher than 100 mmHg at Screening
22. Diagnosis of cholestasis and/or gallbladder sludge/stones

23. History of esophageal bleeding within the last 3 months prior to screening
24. Severe hepatic encephalopathy (Grade >2) or degree of central nervous system impairment which the Investigator considers sufficiently serious to interfere with the informed consent, the conduct, the completion, the results of this trial, or constitutes an unacceptable risk to the subject
25. History of liver transplantation
26. Advanced ascites and ascites which require emptying and/or albumin supplementation within 30 days prior to Day 1, or during the course of the trial, as judged by the Investigator
27. Hemoglobin concentration <100 g/L (10 g/dL)

6. TRIAL ASSESSMENTS AND PROCEDURES

Trial procedures and the times for each assessment are presented in the Schedule of Events Table ([Table 1](#)).

The Investigator, or a person designated by the Investigator, will obtain the written ICF from each subject before any trial-specific activity. Subjects will be provided with abundant time to read and ask questions about the ICF. Subjects will also be provided with a copy of the signed and dated ICF.

6.1. Screening Procedures

Subjects will be screened within 28 days prior to administration of apaglutide to confirm that they meet the subject selection criteria for the trial. The following assessments will be completed during Screening ([Table 1](#)):

- Informed consent
- Instruct subjects on lifestyle requirements and restrictions
- Obtain medical history, including history of prior recreational drug, alcohol, and tobacco use
- Obtain complete medication history for all prescription or non-prescription drugs, and dietary and herbal supplements taken within 28 days prior to the planned dose
- Collect demography (subject race, ethnicity, birth year, age, sex)
- Conduct a full physical examination; this must be performed by trained medical personnel at the CRU
- Collect height and weight
- Collect blood and urine samples
- Determine Child-Pugh score
- Conduct serum and urine pregnancy test for women of childbearing age
- Contraception check

This document is proprietary to VectivBio and for restricted circulation and access only.

- Obtain serum estradiol and FSH in postmenopausal females with amenorrhea ≥ 12 months and under 60 years of age who are not using hormonal contraception or hormone replacement therapy
- Urine drug and/or alcohol test
- Collect 12-lead ECG in triplicate after supine rest of 10 minutes or per CRU standard operating procedure
- Obtain a supine blood pressure and heart rate after at least 5 minutes of rest in a supine position. Repeat measurements may be allowed for safety reasons at the discretion of the Investigator
- Obtain body temperature
- Collect blood for HIV, HBsAg, HB core, and HCV core Ab testing
- Safety laboratory tests
- Adverse event and SAE monitoring

